2.1 Hypotheses & Aims

Our central hypothesis is that preterm children who were randomized to 180 days of DHA+AA at age 1 will exhibit poorer general cognitive ability, greater language deficits, and more impaired executive function at age 8½ -10½ vs children randomized to placebo. Our hypothesis has been formulated primarily on the findings from Omega Tots and DINO, the largest DHA-supplementation trial of preterm infants. The rationale for this project is that a careful examination of the long-term effects of DHA+AA supplementation will offer much-needed clarification about the appropriateness of DHA+AA as an intervention to promote neurodevelopment among children born preterm. We plan to pursue our central hypothesis and accomplish our objective by pursuing the following specific aims:

Aim 1: Determine the long-term effect of DHA+AA supplementation at age 1 year by comparing general cognitive ability, language, and multiple facets of executive function between the DHA+AA and placebo arms at age 8-9.

- Based on our preliminary data, working hypothesis 1 is that children randomized to DHA+AA at age 1 will display at least a 0.3-SD (effect size) deficit on measures of general cognitive ability, language, executive function at age 8½ - 10½ vs placebo.
- Sub-aim 1: Explore sub-group differences by sex, birthweight, socioeconomic status, and diet.

PROTOCOL TITLE: Long-term Effects and Safety of DHA+AA Supplementation in Toddlerhood for Children born Preterm

Aim 2: Determine the role of variability in fatty acid metabolism genetics en masse on the effect of DHA+AA supplementation on short and long-term outcomes, and further focus on 2 previously published FADS2 genetic variants.

- Based on prior observational studies, working hypothesis 2a is that common genetic variant-based heritability over long-chain fatty acid metabolism will be associated with poorer performance on our outcome assessments at ages 1, 2, and 8½ - 10½ years for children assigned to DHA+AA vs placebo. Genetic variation is based on measured SNPs in genes accounting for virtually all synthesis of very long-chain fatty acids. Further, we hypothesize (2b) that minor allele status for FADS2 rs1535 and rs174575, the most commonly replicated SNPs in the literature, will be associated with poorer outcomes for children assigned to DHA+AA, vs placebo.

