6.0 Procedures Involved*

6.1 Study Design

This is a prospective cohort, built from our randomized, blind, placebo-controlled Omega Tots trial of DHA+AA supplementation for 180 days involving children 10-16 months of age (adjusted for prematurity) at enrollment. Participants are Nationwide Children's Hospital (NCH; Columbus, OH) former NICU patients born at <35 weeks' gestation (n=377). All 377 randomized children will be eligible for in-person follow-up at age 8½ - 10½, even those with missing data from the trial, per intent-to-treat. All investigators (except the Principal Investigator and biostatistician), study staff, clinic staff, parents, and children will remain blind to the child's treatment assignment.

The cohort study will be conducted at NCH. There are no collaborating sites where enrollment or data collection will be performed. To recruit families, an attractive "mailer box" will be sent to all eligible families. A Recruitment and Retention (R&R) Specialist (part of the study team at NCH) will call families approximately 1 week post-mailer to further describe the study and gauge child and caregiver interest. Non-responsive or "hard to reach" families will be contacted with further, well-honed attempts by the R&R Specialist. Participation or refusal to participate in the study will not affect entitlement to clinical care.

Children and a parent/guardian will come to NCH when the children are between 8 years, 180 days and 10 years, 180 days, and provide written consent/assent. It is expected that participant enrollment will begin by August 2021, and that human subjects' activity will be completed by February 2025.

Visits will occur in the Center for Biobehavioral Health, child-friendly observation rooms (x8) with video recording equipment built for assessment, observation, and interviews. Trained, experienced staff will carry out the visits 7 days/week including evenings for family convenience. Proposed visit length is approximately 161 minutes.

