17.0 Data Management and Confidentiality

17.1 Data analysis plan

Statistical power and sample size for Aim 1:

All 377 children randomized in Omega Tots will be eligible for follow-up. We estimate power based on a conservative estimate of 300 children (80%) attending the age 8 ½ - 10 ½ visit. To evaluate differences between the treatment arms, 300 children divided equally to each arm provides >80% power to detect a 0.32-SD mean difference or larger (Cohen's $d \geq 0.32$) in each of our primary outcome measures: DAS-II GCA (general cognitive ability), CELF-Core Language (language), or Toolbox Executive Function factor (EF) ($\alpha=0.05$) at age 8 ½ - 10 ½ (Hypothesis 1). This effect size is the same or smaller than what the DINO trial observed on the BRIEF at age 7, and the short (ECBQ) and follow-up (DP-3 at age 2) results from Omega Tots. These effect sizes are also similar in magnitude to the (beneficial) effect observed in the Infant Health and Development Program early intervention trial at age 8 on IQ and reading and math achievement among infants born at 2000-2500g. Sub-group analyses will necessarily be exploratory because only a much larger sample would be fully powered to test the interactions of interest. But, these are worth exploring because in the original Omega Tots trial we observed 2 statistically significant sub-group effects. Although it would be ideal to employ a repeated measures analysis using the 3 available time points (trial, age 2, age 8 ½ - 10 ½), robust developmental measures that are comparable at all time points are not available. We will pursue longitudinal analyses for the secondary outcomes where repeated measures exist, however.

Statistical analysis for Aim 1:

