Analyses for Aim 1 will follow intent to treat principles, the most rigorous approach to RCT data. By using intent to treat we are able to detect lasting effects of DHA+AA supplementation if they are present at the magnitude we anticipate. Children who were randomized but discontinued taking treatment or were lost to follow-up will be included in analyses. Our main goal will be to estimate the effect of treatment assignment on our 3 primary outcomes at age 8½ - 10 ½ (DAS-II GCA, CELF-5 language, Toolbox EF) using the following mixed model, consistent with the analysis of our Omega Tots trial: $y_{it} = \beta_0 + \beta_1 Time_t + \beta_2 Time_t \times Trt_i + \epsilon_{it}$, where implicitly it is assumed that there is no main effect of Trt_i , y_{it} is the outcome of interest at time t , $Time_t$ is coded as 0 for the outcome at baseline (i.e., the covariate for our purposes here) and 1 for the post-randomization measure of the outcome obtained at age 8 ½ - 10 ½, and the primary effect of interest is β_2 , which corresponds to the difference between groups on the outcome at age 8 ½ - 10 ½. In this model, the baseline measure of the outcome is constrained to have equal means across groups by assuming there is no main effect of the intervention, Trt_i . This constraint yields a statistical test for β_2 analogous to the test of the treatment group main effect via ANCOVA controlling for the baseline measure without requiring list-wise deletion due to missing data. Specifically, our model is estimated using maximum likelihood estimation, and therefore allows for outcome data at either time point to be missing at random. We will account for clustering due to twins/triplets in our sample by adding a random effect at the family level. Exploratory pre-specified sub-group analyses will proceed by testing interaction terms added to the models for sex, birthweight (<1500g vs ≥ 1500 g), socioeconomic (household income dichotomized at the median), and daily dietary intake of DHA plus EPA (below vs above the median).

PROTOCOL TITLE: Long-term Effects and Safety of DHA+AA Supplementation in Toddlerhood for Children born Preterm

Interactions with $p < .20$ will be considered statistically significant, and stratified results will be reported consequently. Analyses will use the MIXED procedure, SAS 9.4.

Statistical power, sample size, and analysis for Aim 2 (i.e. genetic biospecimens):

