To address the first part of Aim 2, we apply the standard method for estimating SNP-based heritability, which assumes the common SNP effect is a random effect in a mixed linear model and with variance decomposed into variance components for genetic and non-genetic effects. The generic model is therefore specified as: $y = \beta_0 + X\beta + g + \epsilon$, where g is the random genetic effect and further the model is constrained by $V = A\sigma_g^2 + I\sigma_e^2$ where V is the overall variance decomposed into genetic and non-genetic (i.e. environmental) components; the matrix A is the genetic relationship matrix, which is similar to the concept of a distance matrix in geospatial modeling, though in this case the distance is genetic similarity calculated from the genome-wide SNP data. Therefore, genetic effects are associated with the covariance matrix for common SNPs (called A) and non-genetic effects with the identity matrix (called I). Using the identity matrix for this purpose assumes no shared environment effects, which is valid since only unrelated persons are included in the calculation. We routinely assess age, sex, and socioeconomic status as covariates, and always include ancestry principal components. SNP-based heritability can be performed on case-control datasets, population cohorts or other collections of unrelated individuals. Thus, while traditional heritability assumes zero genetic covariance between “unrelated” persons, observed SNP-based genetic covariance will rarely if ever be zero. The cohort includes mostly unrelated individuals (55 sets of twins/triplets). Rather than model the relationships among related individuals and lose power from increased degrees of freedom, we will apply a resampling procedure. Sampled datasets with 1 twin chosen at random ensures the datasets in each replicate contain only unrelated persons but the average over the sampled datasets converges on estimates that use information from all children. In our cohort we will have $>80\%$ power to detect SNP-based heritabilities as low as 21%, after accounting for the resampling procedure. While fatty acid markers have not explicitly been tested this way before, the relationship between genetics and many metabolism biomarkers in blood is much higher than a heritability of 21%, giving further reassurance that the study is adequately powered. The test of *en masse* SNP effects in the context of this clinical trial takes the form similar to Aim 1, $y_{it} = \beta_0 + \beta_1 Time_{it} + \beta_2 Trt_{it} + \beta_3 g + \beta_4 Trtxg + \beta_5 Timexg + \beta_6 Time_i Trt_i + \beta_7 Time_i x Trtxg_i + \epsilon_{it}$, while the constraints on V are still imposed. The matrix A will be estimated using the software GCTA and the model will be tested using R or Python depending on whether numerical issues arise in the numerical matrix calculations. We can perform this model using structural equation models implemented in the R library genomicSEM. This modeling platform will allow us to use *en masse* SNPs in the models described above.

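### The Aim 1 primary model adjusts only for an unnamed baseline measure and leaves out sex and birthweight as main effects, giving up some precision

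*Combined protocol and SAP*

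**What the plan says.** Section 17.1 (statistical analysis for Aim 1) specifies the analysis of general cognitive ability, language and executive function "using the following mixed model, consistent with the analysis of our Omega Tots trial". The fixed part is an intercept, Time and Time by treatment, and a family random effect is added for twins and triplets. The time-0 response is a baseline measure of the outcome. The arms are constrained to a common mean at that point, so the test behaves like an ANCOVA on baseline. No baseline instrument is named for any of the three primary outcomes.

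The same section brings in sex, birthweight (split at 1500 g), household income and dietary intake, but only as interaction terms in exploratory subgroup models. Continuous secondary outcomes follow the Aim 1 model.

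Three other places bear on the point:

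- Section 6.1 schedules the visit "when the children are between 8 years, 180 days and 10 years, 180 days", a two-year window.
- Section 4.1 makes the cognitive and language outcomes standard scores. It does not say whether the executive function factor is built from age-corrected or uncorrected Toolbox scores.
- The Aim 2 heritability part of section 17.1 says "We routinely assess age, sex, and socioeconomic status as covariates". The Aim 1 model has no such statement.

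**The concern.** Sex and birthweight are fixed before randomisation, are already used in the plan, and may predict cognition and language in children born preterm. Entering them as main effects would normally narrow the interval for the treatment effect. As written, the only variance reduction comes from a baseline measure taken at 10 to 16 months corrected age (section 10.0), which the plan does not identify. A reader cannot judge how much it will help.

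Precision matters here for three reasons. The cohort is capped at 377, so sample size cannot be raised. Section 2.1 hypothesises "at least a 0.3-SD (effect size) deficit on measures of general cognitive ability", slightly smaller than the difference used for power. The same section expects the study either to reassure about safety or to flag lasting harm, so interval width decides how much a null result can say.

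Section 6.1 also states that the principal investigator and the biostatistician are not blind to assignment. Covariates should therefore be fixed in writing and not chosen during analysis.

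**Working it through.** **Inputs from the documents**

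- Sample: "conservative estimate of 300 children (80%) attending", which is 300/377 = 79.6%, with 150 per arm.
- Alpha is 0.05 per outcome. Sidedness is not stated; two-sided is assumed.
- Planning difference: "0.32-SD mean difference or larger". Working hypothesis: 0.30 SD.
- The variance explained by the baseline measure or by covariates is not given.

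Family clustering is ignored throughout. The plan's own power statement does not mention it.

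**The plan's figure.** The standard error in SD units is sqrt(2/150) = 0.1155. At 0.32 SD, 0.32/0.1155 = 2.771; subtracting 1.960 gives 0.811, and power is 79.1% (78.9% by noncentral t). The difference detectable with 80% power is (1.960 + 0.842) × 0.1155 = 0.3235 SD. The statement that "300 children divided equally to each arm provides >80% power" therefore reproduces to within rounding, although strictly it falls just short.

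**At the hypothesised effect.** 0.30/0.1155 = 2.598; subtracting 1.960 gives 0.638, and power is 73.8% (73.6% by noncentral t). This sets the contribution of the baseline measure to zero.

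**Adding covariates.** Let R² be the extra share of follow-up variance explained. The standard error becomes 0.1155 × sqrt(1 − R²), and the study behaves like one of 300/(1 − R²) children. Power is by noncentral t.

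| Assumed extra R² | Standard error | Equivalent children | Power at 0.30 SD |
|---|---|---|---|
| 0 | 0.1155 | 300 | 73.6% |
| 5% | 0.1125 | 316 | 75.7% |
| 10% | 0.1095 | 333 | 77.9% |
| 20% | 0.1033 | 375 | 82.5% |

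The standard error falls by 1 − sqrt(1 − R²), that is 2.5%, 5.1% and 10.6%. Charging up to eight degrees of freedom for the extra parameters changes power by less than 0.1 point.

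**What the baseline measure may already supply.** With an assumed correlation r between baseline and follow-up, R² = r². For r = 0.3 (9%) power at 0.30 SD is 77.5%; for r = 0.4 (16%) it is 80.7%. Only variance explained beyond this counts as a gain from sex and birthweight.

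**Age at testing.** If age is uniform over two years, its SD is 2/sqrt(12) = 0.58 years. With an assumed gain of 0.2, 0.4 or 0.6 SD per year, age explains (slope × 0.577)² = 1.3%, 5.3% or 12% of the variance of a score that is not age-corrected. For an age-normed score it explains about none.

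**The case against.** The strongest reply is that the model is already adjusted. The baseline outcome is modelled as the covariate, and a baseline measure can reduce variance without being on the same scale as the follow-up score. This stands: a reader might infer that the primary model has no covariates, and that is not so. A reader might also take the remark that "robust developmental measures that are comparable at all time points are not available" as an admission that no usable baseline exists. In context it explains only why a three-time-point analysis of the primary outcomes is not used. What remains is that the baseline measure is unnamed.

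The age window also invites more than the text supports. Two of the three primary outcomes are standard scores. That these are age-normed is an inference, but the natural one, and age should then add little. For executive function the argument holds only if uncorrected scores are used, which the plan leaves open.

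The Aim 2 sentence is not a contradiction. It concerns a heritability model in which the exposure is not randomised. The Aim 1 model also has a stated reason, consistency with the parent trial.

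Nor is the gain free. Every R² above is assumed, and at 5% the benefit is about two points of power. Two obvious covariates carry risks:

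- The documents do not confirm that trial-entry income was recorded. The parent-report measures collect demographics at the follow-up visit, which is after randomisation.
- Age at testing does not exist for children who never attend. As a subject-level term it would drop the baseline rows that this model was chosen to keep.

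These points limit the remedy. They do not remove the case for sex and birthweight.

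**Conclusion.** The point holds as a modest matter of efficiency and specification. The primary model leaves out sex and birthweight as main effects and relies on an unnamed baseline measure, in a study with about 74% power at 0.30 SD before baseline adjustment. Under assumed extra R² of 5% to 20%, power at 0.30 SD rises by about 2 to 9 points. Where it lands depends on how much the baseline measure already explains, and the documents do not say.

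A reader might infer that the treatment estimate is biased without these terms. Under randomisation their omission does not by itself cause bias. A possible second benefit is that covariates related to attendance could make the missing-at-random assumption more plausible, with about 20% expected not to attend. The documents give no basis for putting a size on that.

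**What to change.** Change the Aim 1 text in section 17.1 before any comparison by arm:

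- Name the baseline measure used for each primary outcome.
- Add sex and continuous birthweight as fixed effects, each with a Time interaction, in the primary and secondary models. Add household income in the same way only if a trial-entry value exists.
- State that the executive function factor is built from age-corrected Toolbox scores.
- For outcomes that are not age-normed, add age at testing on the follow-up row only, for example as centred age by Time. Code the term directly as zero on baseline rows, so that a missing age does not delete a non-attender's baseline record.
- State how missing covariate values will be handled.
- Keep the model as now written as a sensitivity analysis.

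The cost is SAP wording and up to two parameters per covariate: four for sex and birthweight, six with income, and one more where age enters on the follow-up row only. Sex and birthweight are already used in the plan; whether trial-entry income is held needs checking.

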Upon completion of the proposed research, our expected outcomes are to have determined the long-term effects of DHA+AA supplementation in toddlerhood for children born preterm and the role of genetics. These results are expected to have an important positive impact: we expect to either offer reassurance about the safety of DHA+AA-supplemented products for young children, or bring attention to negative long-term effects and, thereby, steer the field to seek alternative interventions and further examine mechanisms for adverse effects.

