The measures administered during this single visit involve combination of computerized and manual tests described in section 6.2. Testing will occur in a fixed order with 2 scheduled breaks unless children lose attention or express the need for a break at other times. The parent will be in an adjacent room completing questionnaires described in detail in section 6.3. Saliva collection will occur using procedures detailed later (see sections 6.2 – 6.5). We will offer the parent a \$100 incentive, parking pass, a small gift or snack (value ~\$5), and a letter summarizing the child's general standardized test results (e.g. average, below average, above average). We will offer the child a \$10 incentive, an age appropriate book, and a small gift or snack (value ~\$5) upon completion of all study components. All study activities and experiences will be documented on appropriate Clinical Research Forms (CRFs), according to NCH IRB standards. If families are unable to complete a study visit at NCH, staff will offer the family the opportunity to carry out the visit in a convenient community location near their home (e.g. library, NCH Close to Home site) or the participants home if absolutely necessary. If none of these is possible the family can become a "survey only" family, where they will not complete an "in person visit," but may still complete surveys either online, via phone or via postal mailed responses, or telemedicine. In these cases, staff will mail out

PROTOCOL TITLE: Long-term Effects and Safety of DHA+AA Supplementation in Toddlerhood for Children born Preterm

a saliva kit including instructions how to give a sample and mail back in provided packaging. Participants will be informed that this “survey only” option is accompanied by partial compensation, but it is again completely voluntary. Staff will emphasize that participation is valued, but if they choose to stop participating there will not be a penalty or loss of benefits to which they are otherwise entitled (e.g. clinical care at NCH).

If “in person” study visits are no longer permitted due to the COVID-19 pandemic or other extenuating circumstances, staff will transition to collecting as much data as possible via the remote means mentioned above for “surveys only” family cases (e.g. phone, online, mail, telemedicine). Staff would also mail out a saliva kit including instructions how to give a sample and mail back in provided packaging.

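### The primary model's missing-at-random assumption rests on little beyond arm; earlier developmental scores should enter as auxiliaries

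*Combined protocol and SAP*

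**What the plan says.** Section 17.1 starts from "All 377 children randomized in Omega Tots will be eligible for follow-up", then plans on fewer: "We estimate power based on a conservative estimate of 300 children (80%) attending". The Aim 1 analysis is described as intention-to-treat, and children lost to follow-up are said to be included. The model uses two records per child, a baseline measure of the outcome and the measure at 8½ to 10½ years. Baseline means are constrained equal across arms, and a family random effect handles twins and triplets. Likelihood estimation "therefore allows for outcome data at either time point to be missing at random".

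On using the intermediate time point, the power paragraph says "robust developmental measures that are comparable at all time points are not available" and keeps longitudinal analyses for secondary outcomes. The later Repeated measures paragraph of 17.1 says the Aim 1 analyses will be extended where the same or a similar measure was repeated, and gives a global cognitive composite as an example.

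Under section 6.1, families who cannot attend "may still complete surveys either online, via phone or via postal mailed responses, or telemedicine". No auxiliary variable, imputation, weighting or missing-data sensitivity analysis is specified for the primary outcomes.

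**The concern.** Missing at random is only as credible as the variables it conditions on. Here these are arm, one baseline score and, for a minority, a sibling's score (17.1 counts 55 twin or triplet sets).

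Even the baseline score is in doubt. Children were enrolled at 10-16 months, and section 6.2 gives the Toolbox range as 3-85 years, so the executive function factor cannot have been measured at trial entry. No baseline counterpart is named for the DAS-II or CELF-5 either. Without one, a child who misses the visit has no record in the model, which sits badly with the statement that children lost to follow-up will be included.

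The cohort has relevant earlier data: sections 3.0 and 17.1 describe end-of-trial results and an age-2 developmental score. Lack of comparability is a reason not to fit a common repeated-measures outcome. It is no reason to leave a score out as an auxiliary, which need only predict the outcome or attendance and need not share the outcome's scale.

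This matters because a null result will be used: "we expect to either offer reassurance about the safety of DHA+AA-supplemented products for young children". If attendance depended on earlier development differently in the two arms, the comparison of attenders would be distorted.

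**Working it through.** **Inputs from section 17.1.** 377 randomised; 300 expected to attend; d = 0.32; alpha 0.05 (two-sided assumed). Non-attenders: 377 − 300 = 77, a fraction of 77/377 = 0.204.

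**The plan's own figure.** The plan says "300 children divided equally to each arm provides >80% power to detect a 0.32-SD mean difference or larger". With 150 per arm, 0.32/√(2/150) = 2.77; 2.77 − 1.96 = 0.81; power = 79.1%. That reproduces the claim to within a point, though not strictly above 80%.

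**Assumptions not in the documents.** Age-2 score correlated 0.4 to 0.6 with the outcome for bias, and 0.3 to 0.7 for precision. Attendance logistic in the age-2 score. Age-2 arm difference of −0.3 SD, the size reported in section 3.0. No usable baseline score.

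**Bias.** In each arm the attenders' mean is shifted by

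fraction missing × r × (attender minus non-attender gap in age-2 score, in SD),

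and the bias is the difference between arms. Log-odds slopes of 0.4, 0.8 and 1.2 per SD give gaps of about 0.39, 0.73 and 0.98 SD at 79.6% attendance. With equal attendance in the two arms:

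- Same slope in both arms: the shifts cancel, so bias is 0.
- Slopes 0.8 and 0.4: 0.204 × (0.73 − 0.39) = 0.069; times 0.4 to 0.6 gives 0.03 to 0.04 SD.
- Slope 0.8 in one arm, 0 in the other: 0.204 × 0.73 = 0.149; times 0.4 to 0.6 gives 0.06 to 0.09 SD.
- Slope 1.2 in one arm, 0 in the other: 0.204 × 0.98 = 0.200; times 0.4 to 0.6 gives 0.08 to 0.12 SD.

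If one intercept is used for both arms, the arm with lower age-2 scores attends less often and the figures rise. Equal slopes of 0.5 to 1.2 give 0.004 to 0.026 SD. Slopes 0.8 and 0.4 give 0.04 to 0.06 SD, and 1.2 and 0.8 give 0.045 to 0.07 SD. A slope of 0.8 or 1.2 in the DHA+AA arm only gives 0.07 to 0.15 SD.

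The sign follows the assumption. Low scorers staying away only in the DHA+AA arm would hide a deficit; the same pattern only in the placebo arm gives the opposite sign.

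A simulation with one million children per scenario (baseline correlation 0.2, age-2 correlation 0.3 to 0.7) left at most about 0.006 SD of bias once the age-2 score was used within arm. That holds because attendance was made to depend on that score alone.

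**Precision.** Variance factor = 1 − r² × m/(n + m), with n = 300 attenders and m the non-attenders who have the auxiliary.

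| m | r | variance factor | SE falls | effective N | power at 0.32 SD |
|---|---|---|---|---|---|
| 77 | 0.3 | 0.982 | 0.9% | 306 | 79.9% |
| 77 | 0.5 | 0.949 | 2.6% | 316 | 81.2% |
| 77 | 0.7 | 0.900 | 5.1% | 333 | 83.2% |
| 38.5 | 0.5 | 0.972 | 1.4% | 309 | 80.3% |

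**The case against.** The constrained likelihood model is an accepted method and matches the original trial. Attrition is tackled by design: community and home visits, a second mailing, and a refusal questionnaire. The Repeated measures paragraph may already bring age-2 data in for global cognition. All this stands, but none of it names an auxiliary for language or executive function, and that paragraph is hard to square with the power paragraph.

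Three stronger readings are tempting and should be resisted.

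- A reader might infer that the trial is biased towards false reassurance. The documents do not show that attendance depends on earlier scores, still less differently by arm. Parents, children and study staff remain blind, which makes arm-specific dependence less likely. The offered letter on test results could as easily draw families of struggling children.
- A reader might infer that caregiver ratings are in hand for every child who misses the visit. They are new follow-up measures, available for such children only if the family chooses the survey-only option. The number of non-attenders with an age-2 score is not given either.
- A reader might take the power paragraph as conceding that no earlier measure exists. It says only that comparable measures are lacking across all time points.

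The assumed correlations are also unsourced. Section 3.0 notes that the earlier adverse findings were parent-reported, whereas the primary outcomes are directly tested years later.

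**Conclusion.** The point holds as a cheap improvement, not as a demonstrated flaw. As written, the primary analysis conditions on arm, a baseline score that may not exist for these outcomes, and any observed co-twin. The stated reason for omitting age 2 does not rule out its use as an auxiliary.

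Possible bias is about 0 to 0.025 SD under equal dependence in both arms. It is about 0.03 to 0.06 SD with moderately different slopes (0.02 to 0.07 SD across those tried), and 0.06 to 0.15 SD only under strong dependence in one arm. Against the 0.32-SD target, the last range is 19% to 47% (0.06/0.32 and 0.15/0.32), but it is a stress case. Direction is unknown. The gain in precision is minor: about 1 to 4 power points if every non-attender has the auxiliaries, and less otherwise. All bias figures rest on the assumed correlation of 0.4 to 0.6 and the logistic attendance model.

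**What to change.** For each primary outcome, add these auxiliaries: end-of-trial and age-2 developmental scores, birthweight, gestational age, sex, household income at trial entry (if recorded then) and, where returned, survey-only BRIEF-2 and CBCL. Use either joint maximum likelihood or multiple imputation within arm, and make the method respect twin and triplet clustering. The end-of-trial, age-2 and follow-up caregiver scores are post-randomisation, so they may serve as auxiliaries or joint outcomes but must not be adjustment covariates.

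Report the present model alongside. State what baseline measure, if any, pairs with each primary outcome. Reconcile the power and Repeated measures paragraphs of 17.1 on whether extra time points apply to the primary outcomes.

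Cost: a paragraph in the analysis plan and routine programming, with no new data. The downside is a somewhat more complex analysis.
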